Primary Specific Aim 2 Hypothesis 1 (Mediation Hypothesis). Decreases in DD will be significantly associated with decreases in HbA1C within each of the 3 intervention groups over 12 months. Associations between changes in DD and changes in glycemic control will be explained by changes in disease-management mediators (e.g., increased blousing) across all 3 intervention groups. In exploratory analyses, we will examine the direction of associations as presented in the conceptual models in Figure 3.

Secondary Specific Aim 1 Hypothesis 1 (Moderator Hypothesis). Differences in primary and secondary outcomes between FixIt and TunedIn will be qualified by: (a) patient characteristics (with stronger positive effects for younger age and patients with shorter T1D duration), (b) both baseline emotion regulation (ER) skills and level of DD (with stronger positive effects for patients with poorer ER skills and higher DD), and (c) baseline cognitive-processing constructs (with stronger positive effects for patients with lower problem-solving skills and diabetes knowledge).

Secondary Specific Aim 2 Hypothesis 1 (Cost-effectiveness). FixIt and TunedIn will be more cost-effective than StreamLine in terms of improvements in primary and secondary outcomes.

Research Design: This is a 3-arm, 12-month randomized comparison trial (baseline N=118 per arm) to test the added value of a DD-targeted intervention (TunedIn) vs. a unified DD and management intervention (FixIt), relative to a traditional, educational/behavioral-management intervention (StreamLine) to reduce diabetes distress and improve glycemic control in adults with type 1 diabetes. Additionally, the implementation costs and per-participant program costs will be calculated.

Each of the 3 arms will follow a separate, standardized protocol. All participants will receive 3 months of intervention with 9 months of follow-up (12 months total).

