In summary, (i) few studies have measured DD directly and have identified the explicit sources of DD among T1D adults; (ii) the content of interventions have often been focused solely on education and behavior change, with DD change often considered a secondary outcome; (iii) no studies have used an integrated framework that addressed DD-related emotions and cognitions, and none have addressed how they directly influenced diabetes management and glycemic control; and (iv) very few studies included T1D adults with high baseline DD and HbA1C, making it difficult to identify interventions that reduce both DD and HbA1C and determine their relationships. This study builds upon this literature by addressing each of these issues directly.

Recruitment. Adults with T1D will be recruited by partnering with academic clinics' research registries and community-based organizations. Partnering organizations will send e-mails and/or social media posts to their members. Patients who are eligible and interested during telephone screening will be emailed a link to a secure electronic consent and online baseline survey, with a copy of the consent emailed for their records. Patients who are eligible following completion will be sent a pre-paid slip to

collect HbA1C at a local laboratory to confirm HbA1C eligibility. HbA1C collection will be 5.0ml of whole

Follow up will occur at 3, 6, and 12 months following Group Meeting 1, and procedures will be the same for each group. Participants will be emailed a link to a secure online follow up survey, plus a pre-paid slip to collect HbA1C at a local laboratory. HbA1C collection will be 5.0ml of whole blood.

Interventions:

1. **StreamLine** (management strategy)
2. **TunedIn** (DD-targeted strategy)
3. **FixIt** (unified strategy)

Each of the 3 study arms will selectively include: (a) a group workshop (8-10 participants), (b) real-time online video group meetings and (c) individual phone/video calls or face-to-face meetings with the interventionist (summarized in Table 1).

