TunedIn (DD-targeted strategy) utilizes exercises and scenarios of ER-based strategies that were effective in reducing DD in the OnTrack arm of T1REDEEM6, now greatly expanded in number and focused in intensity to be more comprehensive and inclusive to help participants observe how what they feel affects what they do regarding disease management. Taking advantage of the power of facilitated group interaction in reducing DD, participants in TunedIn will attend 2 highly interactive group workshops (6 hours followed by 2 hours), facilitated by a psychologist or social worker experienced in diabetes. Each will identify and discuss common emotional responses related to BG management (e.g., over-reacting, avoiding, lack of mindfulness). Between the two workshops (2 weeks), participants will

blood. For those patients who are unable to go to a local laboratory, we will provide a HbA1C home test kit mailed to their home address for their convenience and comfort. After blood sample is provided by patient (instructions are provided in each test kit), they will mail the kit back to the lab to be analyzed. Randomization of eligible participants will occur after baseline assessments. Sequential ID numbers will be generated and randomly assigned to the 3 study groups. Each participant will receive the next ID number, contained in a REDCap database. Block randomization stratified by clinical recruitment site will be used to ensure equivalent distributions in the three intervention study arms across sites. complete a "feeling log," a tool commonly used in ER-based programs, in which participants document.

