Data Analysis. Descriptive statistics will be computed for baseline characteristics, initially testing for differences between: (1) intervention arms and (2) patient dropouts vs. non-dropouts. Patient-level demographic and disease status covariates will be screened in bivariate analyses and included in multivariate analysis if they are related to the outcome at $p < .20$, significantly differ between treatment arms, or are associated with dropout. Correlations among variables within each area of secondary outcomes and moderators (see measures above) will be examined, and redundant measures will be combined or eliminated to avoid multicollinearity. In the event normality assumptions are not met, we will use transformations to normalize distributions, ordinal or Poisson regression where appropriate, and/or the appropriate link function (e.g., logit link for dichotomized measures)⁹⁵⁻⁹⁷. We will examine change in outcomes across groups will be evaluated by ANCOVA. In these models, the follow-up value is specified as the outcome, the baseline value as the covariate, and treatment group was a fixed effect. When the treatment group effect was statistically significant ($p < 0.05$), Helmert contrasts will be used to determine differences among the three groups. Missing values will be imputed with NORM software (version 2.0; The Methodology Center, Penn State, University Park, PA) (23,24) using multiple-imputation procedures to create a stable, complete data set. Parallel analyses will be performed with raw and imputed data sets. Hypothesis tests will be 2-sided with alpha set at .05. Goodness-of-fit tests and model-fitting diagnostics will be used to assess for influential points, outliers, over-dispersion, and heteroscedasticity, and to evaluate alternative model specifications.¹⁴³

Intervention implementation costs on a per-participant basis, and training costs on a per-facilitator basis, will be calculated using activity-based costing methods. Costs for staff time will be assigned based on the prevailing national wage rate as reported in the Bureau of Labor Statistics' Occupational Outlook Handbook in the final year of intervention implementation⁹². All other costs will be adjusted for inflation

to constant U.S. dollars for the final year of implementation using the Bureau of Labor Statistics'

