Sample size and power estimates are based on two-sided $\alpha = 0.05$ and Student t tests on change from baseline to each follow-up point. Estimating a 20% attrition rate, a sample of 90 per group allows for detection of moderate effect sizes ($d = 0.47$ SD unit differences) equating to mean changes in DD of at least 0.36 and mean changes in HbA1c of at least 0.44%.

Inclusion criteria:

To be eligible to enter baseline assessment:

- Adult patients with T1D (confirmed by clinical history and/or anti-glutamic acid decarboxylase [GAD] antibody testing) on intensive insulin treatment;
- Diagnosis of T1D for at least 12 months that occurred at or below age 40;
- Age 19 years or older;
- Have a recent HbA1c of 7.2% or higher, or unable to recall most recent value;
- Not have started to use any new (to the participant) diabetes device (such as an insulin pump or continuous glucose monitor) in the past 6 months;
- Internet access through a computer or smart phone;
- Ability to speak/read English.

To be eligible to be randomized to receive an intervention (following baseline assessment):

- Type 1 Diabetes Distress Scale (T1DDS) mean score 2.0 or higher;
- HbA1c 7.5 or higher.

Exclusion criteria:

- Documented psychosis, blindness, dementia, active dialysis, substance abuse, amputations, or severe functional deficits, or recent major surgery or hospitalization in the past year.

Consent process

During the telephone screening call, patients will be invited to give verbal consent to be screened for eligibility. Verbal consent will be documented by the researcher. Following determination of eligibility and interest, the study protocol will then be described to individuals. During the initial recruitment conversation, potential participants will be asked open-ended questions and they will be invited to repeat back their understanding of the study. Individuals will then be asked to report their name, mailing address, phone number, and email address.

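### Imputation is described as producing one completed data set with no pooling step; analysed that way at 20% attrition, the gating group test is either too liberal (about 7–14% type I error) or biased towards no difference

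*Combined protocol and SAP*

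**What the plan says.** The missing-data plan is two sentences in the Data Analysis section. Missing values are imputed in NORM 2.0 "using multiple-imputation procedures to create a stable, complete data set", with two cited references. Then: "Parallel analyses will be performed with raw and imputed data sets". The section does not give the number of imputations, the variables in the imputation model, a rule for combining results, or which of the two parallel analyses decides.

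The rest of the analysis is specified: ANCOVA of the follow-up value on baseline and treatment group, two-sided alpha 0.05. If the group effect reaches p < 0.05, "Helmert contrasts will be used to determine differences among the three groups". Covariates enter if they are related to the outcome at p < 0.20, or if they "significantly differ between treatment arms, or are associated with dropout".

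Three other statements set the scale:
- Research Design: "baseline N=118 per arm".
- Sample size paragraph: "Estimating a 20% attrition rate", with a detectable difference of 0.47 SD.
- Recruitment section: "Follow up will occur at 3, 6, and 12 months following Group Meeting 1". Some dropouts may therefore have interim values that can inform the imputation.

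**The concern.** Multiple imputation gives valid inference because the spread between completed sets is added to the within-set variance. The plan states its product in the singular and describes no step that does this. An analyst who follows the text would fit one ANCOVA to one filled-in set, and the model would count about 24 imputed values per arm (0.20 × 118 = 23.6) as if they had been measured.

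That analysis fails whichever imputation model is used. With arm in the model, the standard errors are too small and the group test rejects too often. With arm left out, imputed values carry no arm difference beyond what baseline and any interim values convey, so real differences shrink. The group test is the gate to the contrasts for both primary outcomes, HbA1c and Diabetes Distress, so either fault bears on Aim 1.

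**Working it through.** **Inputs from the plan.** Alpha 0.05 two-sided; 2-df group test as gate; 118 per arm; 20% attrition; d = 0.47; visits at 3, 6 and 12 months.

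**Assumed.** Data missing completely at random, equally in each arm; normal outcomes; baseline–outcome correlation 0.5; interim–final correlation 0.6–0.9.

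**The plan's own figure.** The plan gives no error rate for the imputed analysis. Its sample size reproduces if power is taken as 80% (not stated): 2 × (1.960 + 0.842)² / 0.47² = 71.1, so 72 per group, and 72 / 0.80 = 90. The result below is the same at 90 or 118 per arm.

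**Formula, arm in the imputation model, no interim data.** Let L = 0.20 be the missing fraction and R the true variance of the arm estimates divided by the variance the ANCOVA reports. For a 2-df test in large samples, type I error = 0.05^(1/R).
- One draw with parameter uncertainty: R = 1 + 2L/(1 − L) = 1 + 0.40/0.80 = 1.50, so 0.05^(1/1.50) = 13.6%.
- Many draws averaged into one set: R = 1/(1 − L)² = 1/0.64 = 1.5625, so 0.05^(1/1.5625) = 14.7%.

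Neither depends on the assumed baseline correlation.

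**Simulation.** 6,000 null trials per setting, 118 per arm, 20 imputations for pooling; Monte Carlo SE about 0.3 points at 5% and 0.44 at 14%. The table shows type I error of the group test at 20% missing. A dash means no separate figure is listed.

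| Dropouts with an interim value | One set, arm in | One set, arm out | Pooled (D1) | Raw |
|---|---|---|---|---|
| None | 13.6% | 5.0% | 5.1% | 4.8% |
| Half, correlation 0.6–0.8 | 11.4–13.2% | 4.7–5.3% | – | – |
| All, correlation 0.6 | 11.8% | 4.6% | 4.6% | 4.8% |
| All, 0.7 | 9.6% | 4.8% | 4.8% | 4.5% |
| All, 0.8 | 8.8% | 5.2% | 5.3% | 5.0% |
| All, 0.9 | 7.2% | 5.5% | 5.6% | 5.1% |

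Averaging 20 draws into one set gave 14.6% with no interim data. Separate runs using both interim visits gave 6.8–11.8% when all dropouts had them, and 9.6–11.4% with gradual dropout (10/15/20%). At 10% missing with no interim data, the single-set figure is 8.4%.

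**Cause.** For TunedIn minus StreamLine with no interim data, the single-set analysis reports a standard error of 0.113 SD against a true 0.138. (0.138/0.113)² = 1.49, which agrees with R = 1.50.

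**Contrasts.** On the single-set reading with arm in the model, each gated Helmert contrast is falsely significant in 7.2–7.4% of trials with no interim data and in 4.5–6.3% with interim values for all. On raw data the figure is 2.2–2.8%.

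**Arm left out.** With no interim data, the expected estimate of a true 0.47 is 0.47 × (1 − 0.20) = 0.376. Simulation gave 0.374, about 20% smaller. With interim values for all dropouts it gave 0.420–0.442: (0.47 − 0.420)/0.47 = 10.6% and (0.47 − 0.442)/0.47 = 6.0%. Pooled estimates with arm in the model were 0.466–0.472. Pooling does not cure the omission of arm: with no interim data, pooling without arm rejected in only 1.3% of null trials.

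**The case against.** The strongest reply is that the text names multiple imputation and goes on to speak of imputed data sets, which may be plural. A statistician could fill in the standard practice of pooling, and the cited references may describe it. That stands. A reader might infer that the plan commits to single imputation, or that the trial's group test will have 14% type I error. The documents support neither. The error rates hold only if one set is analysed as observed, and the upper figure also needs arm in the imputation model and dropouts without interim data.

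A reader might also infer that no primary analysis is specified. That goes too far: the ANCOVA, the gate, the contrasts and alpha are all given, and the software is named. What is open is the content of the imputation model, the pooling, and the choice between raw and imputed results.

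Three further points stand in part.
- The raw-data analysis is pre-specified and holds about 5% under the missingness simulated, so a discordant result would be visible. Without a rule for discordance, this is only a partial safeguard.
- The Laboratory Assessments text allows provider HbA1c results to be requested when draws are missed. Missing HbA1c may therefore fall below 20%. No such step is described for Diabetes Distress.
- Individual contrasts are less inflated than the gate. With arm left out, group-test power falls from 97.3% (pooled) to 93.0% with no interim data, but is not lost when all dropouts have interim values (97.8–98.3%, against 97.3–97.5% on raw data). The bias in the estimate remains.

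**Conclusion.** The point holds as a conditional defect in a stated procedure. Followed as written, the text leads to one completed set analysed as observed. At the planned 20% attrition the gate then has about 14% type I error with arm in the imputation model and no interim data, and about 7–12% if every dropout has interim values. With arm left out, the error rate is near 5% but a true 0.47 SD is estimated about 20% too small, or 6–11% too small with interim values for all. Pooling with arm in the model restores about 5% (4.6–5.9% over all runs); raw data give 4.5–5.9%.

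These sizes rest on data missing completely at random, equal attrition by arm and the assumed correlations. Missingness related to outcome or arm was not examined. The wording leaves pooling possible, so the change is a correction of the text and not a finding that the trial's analysis is invalid.

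**What to change.** Replace the single completed data set with wording such as:

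*Several imputed data sets (for example, 20 or more) will be generated from a model that includes study arm, the baseline and all follow-up values of the outcome, and the covariates of the analysis model. The ANCOVA will be fitted in each. The 2-df group test will be pooled by a multi-parameter method (for example, D1) and, if it is significant, the Helmert contrasts will be combined by Rubin's rules.*

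Also name in advance whether the pooled or the raw-data analysis is primary, with the other as a sensitivity analysis.

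The cost is a few sentences and trivial computing. Standard errors will be about 6–13% larger than a single completed set would wrongly report. For TunedIn minus StreamLine at 20% missing, they go from 0.113 to 0.127 SD with no interim data, or to 0.120–0.124 with interim values for all dropouts. The raw-data analysis gives 0.126, so nothing material is lost against it, and interim values bring a slight gain.

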All study procedures are the minimum necessary to meet study objectives, with steps taken to mitigate risks. The research team has sufficient expertise and experience to conduct the research, and the sample size is sufficient to yield useful results.

CONSENT

Consent to participate is an ongoing process. During the initial recruitment conversation when the research assistant describes the study, they will invite participants to ask questions and ask them to repeat back to us their understanding of the study. Participation in the project will not affect the patient's clinical care in any way, and participants may withdraw consent at any point during their involvement.

MEDICAL AND PSYCHOLOGICAL CONCERNS

The protocols for addressing any emerging concerns is described above.

CONFIDENTIALITY

We will only collect the minimal personal information that is absolutely essential to research activity. All information will be coded and securely stored, with access solely granted to the investigators and study staff.

ECONOMIC HARMs

Participants will not bear the costs of any study procedures.

BENEFITS

Possible immediate and/or direct benefits to participants and society at large include:

- Knowledge may be gained about their health and health conditions
- Feeling of contribution to knowledge in the health or social sciences field

Payment

Participants will be paid for each of the 4 assessments (but not for the interventions) using gift cards on an incremental scale, as follows:

Stage	Survey	Labs	Total
Baseline	\$20	\$20	\$40
3 months	\$25	\$30	\$55
6 months	\$30	\$35	\$65

9 months	\$35	\$45	\$80
\$240
